**A.C.Camargo Cancer Center – Brazil**

**Registration Number on Institutional Research Ethics Committee: 3025/20**

**March 2021**

## **Abstract**

Neuroendocrine tumors (NET) are rare neoplasms, which frequently present metastatic and incurable at diagnosis. In this context, few effective therapies exist. When the disease becomes refractory to standard therapies, treatments with limited efficacy (eg, surgical debulking, cytotoxic chemotherapies, interferon alpha) that could lead to important adverse events are used. Therefore, clinical studies that test new therapeutic strategies in NET patients with refractory disease are needed. Treatment with radiopharmaceuticals have been studied in NET and showed to be promisor. As an example, is the treatment with Lutetium^177 octreotate, disponible in Brazil for decades, and one of the most active therapeutic options to NET.

The radiopharmaceutical MIBG-I (metaiodobenzylguanidine linked to Iodine) is the first treatment choice for patients with paraganglioma/pheochromocytoma (PggF), a rare type of neuroendocrine neoplasm originated from neural ganglia. Patients with this neoplasia are submitted to scintigraphy with MIBG-I, a norepinephrine analog whose transporter protein is highly expressed in this tumor. If the uptake is positive, patients receive treatment with therapeutic doses of MIBG-I. The disease control with this intervention could last two years. Old and small studies suggested that MIBG-I could also have an activity in other NET besides PggF. Gastrointestinal (GI) or lung NET could have a positive expression on MIBG-I scan in up to 50% of the cases. With this rationale, retrospective series reported that MIBG-I could offer clinical benefit in patients with GI NET, with disease control in up to 80% of the cases. However, the literature regarding therapeutic MIBG-I to NET not PggF is scarce, heterogeneous regarding population, methods of response assessment, doses of the radiopharmaceutical, and short follow-up time. Therefore, due to the absence of effective therapeutic options for patients with metastatic well-differentiated NET refractory to standard treatments, the evidence that NET can have a positive expression on MIBG-I scan, and that small retrospective studies with a low level of evidence suggest a benefit for control disease and improvement of symptoms, the investigators proposed a phase II study of MIBG-I to well-differentiated GI or lung NET patients with positive MIBG-I scan.

Adult patients, ECOG 0-2, with good organic functions, with progressing metastatic or locally advanced NET of GI or lung origin, with refractory disease or intolerant to available standard therapies, and with positive MIBG-I scintigraphy in metastatic lesions are eligible for receive up to 4 doses of 7,400Mbq (200 mCi) each, with an interval of at least 60 days. The primary outcome will be the disease control rate (DCR) at 6 months after the end of treatment, per RECIST 1.1; secondary outcomes will be DCR at 3 months post treatment, progression-free survival, radiological and biochemical response (functional NET), toxicities and quality of life measured by the EORTC QLQ-C30 and GINET21 questionnaires. Laboratory tests and clinical evaluation will be performed every 2 weeks during the study; Imaging exams will be performed every 3 months until progression. The study sample will be 22 patients. For this calculation, we consider the H0 of DCR in 6 months of 40% (placebo arm of phase III studies in TNE), H1 as 67%. Two-tailed type I error margin of 10%, power of 80% and loss of follow-up/non-adherence of 10% were considered. We estimated a 50% screening failure (50% positivity on MIBG-I).

If the study is positive, it can be cost-effective, as we estimate that 67% of patients will obtain disease control lasting at least 12 months, which will provide time free of toxic therapies with a low level of evidence and costly to patients and paying sources. In addition, the study has the potential to change the treatment guidelines for NET, facilitating the incorporation of MIBG-I as a therapeutic strategy in the treatment protocols for NET at A.C.Camargo Cancer Center. The study, therefore, may allow the institution in the future to offer treatment with MIBG-I to patients with supplementary health, recovering the costs invested in the MIBNET study.

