## **Introduction**

Neuroendocrine tumors (NET) are rare neoplasms, but with increasing incidence and prevalence in the last decades. In more than half of the cases, they present metastatic and incurable at diagnosis. Few effective therapies are approved for these tumors (somatostatin analogues, everolimus, and sunitinib), none have demonstrated gains in overall survival, and none is approved in the Brazilian public health system (SUS).

Well-differentiated NET express, in more than 80% of the cases, somatostatin receptors. Somatostatin analogues, lanreotide or octreotide, have anti-proliferative and anti-secretory activity, and, frequently, are considered the first-line treatment in the metastatic setting. Somatostatin receptors expression, through scintigraphy scan marked with radionuclide and octreotate (Octreoscan©) or positron emission tomography labelled with Ga (Ga-PET-CT), is mandatory to effectively indicate the treatment with Lutetium^177 radionuclide. The NETTER-1 study demonstrated the efficacy of Lutetium^177, a type of peptide receptor radionuclide therapy (PRRT), in combination with long-acting releasing (LAR) octreotide 30 mg in second-line, with progression-free survival of approximately 40 months versus 8.5 months for the group treated only with LAR octreotide monthly in patients with midgut NET metastatic (HR: 0.20;  $p < 0.0001$ ). The NETTER-1 study established one more therapeutic strategy to NET, the PRRT.

However, invariably, metastatic NET patients develop disease progression to standard treatment. Different chemotherapeutic regimens (FOLFOX, cisplatin/etoposide, cisplatin/irinotecan, capecitabine/oxaliplatin, and capecitabine/temozolomide), hepatic debulking surgery, and interferon alpha are used based on small phase 2 trials and/or retrospectives studies. In the Brazilian consensus of NET, these treatment modalities, even with low evidence level, are recommended when there are no other effective treatments available. Although some patients could benefit from these therapeutic options, the results relating to tumor response and quality of life tend to be modest and the toxicity significant (Table 1). Therefore, new treatment should be investigated in this context.

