## **Objectives**

### **Primary:**

- 1 - Control of radiological disease at 6 months after the end of treatment.
- 2- Control of clinical/biochemical (functional NET) at 6 months after the end of treatment.

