### **Statistical plan**

Descriptive statistics will be used to report population characteristics, binary outcomes and adverse events. The Kaplan-Meier method will be used to report time-to-event variables and the reverse Kaplan-Meier method will be used to calculate the follow-up time for patients. For the analysis of quality of life, we will report the proportion of patients who increase the sum of the total score by at least 10% at 3 and 6 months after treatment - improvement of at least 10% is considered to be clinically significant by patients. We will also evaluate whether the global score varies and how much varies during the study for each patient; this analysis will be carried out in percentage and descriptively. The scores will be calculated according to the instruction manual of the EORTC group. The quality-of-life analysis will be carried out using the

intention to treat method, where patients who do not respond will be considered “non-responders” in terms of the effectiveness of the treatment.

Missing data in the questionnaires will be dealt with as described in the section above "Quality of Life Assessment".

The study sample will be 22 patients. For this calculation, we considered the 40-month disease control rate H0 to be 40% (placebo arm of phase III studies in TNE, such as the RADIANT417 study), H1 to 67%. Two-tailed type I error margin of 10%, power of 80% and loss of follow-up / non-adherence of 10% were considered.

We estimated a 40% screening failure (40% positivity on MIBG-I131).

All analyzes will be by intention to treat. Patients who receive at least one dose of MIBGI131 will be evaluated for toxicity and efficacy.

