### **Potential for cost-effectiveness**

Treatment with MIBG-I, in addition to being available at SUS for the treatment of patients with PggF, appears to offer significant disease control for patients with NET. If the study is positive, it can be cost-effective, as we estimate that 67% of patients will obtain disease control lasting at least 12 months, which will provide time free of toxic therapies, with a low level of evidence and costly to patients and paying sources. In addition, in the absence of a clinical study, these toxic and ineffective therapies are used sequentially, so that each patient will do, in the period of 12 months, at least two of them.

**Table 1.** Treatments used in midgut NET or refractory lung, respective toxicities, efficacy and levels of scientific evidence

Treatment	Disease control rate (%)	Time of disease control (months)	Common toxicities	Evidence level
Folfox/Capox	0-10%	4 – 6	Peripheric neuropathy, diarrhea, nausea, vomiting, thrombocytopenia, anaemia	Retrospective, heterogeneous population*
Capecitabine/ Temozolomide	0-10%	4 – 6	Nausea/Vomiting, diarrhea	Retrospective, phase 1/2 with heterogeneous population
Interferon alpha (3 to 6 million units/week)	20 – 30% (symptoms), 50% (radiological)	10	Psychiatric disorders, immunes, fatigue, myopathy, myelosuppression	Phase III for radiological control, retrospective studies for symptomatic control
Debulking hepatic surgery (R2)	50 – 90% (only symptoms)	19 – 45	Surgical risk compared to a hepatectomy	Retrospective, heterogeneous population
MIBG- 	63 – 80%	12 – 24	Myelosuppression	Retrospective, heterogeneous population

\* neuroendocrine tumors of different origin, efficacy measured with distinct criteria

**TABLE 2.** Complete procedural summary of the study after signing the informed consent form

Procedure	Screening *	Baseline evaluation	D1 **	S2 **	S4 **	...	S8 **	S12 **	S16 **	...	S24 **	Every 12 or 8 weeks
Eligibility assessment												
MIBG scan	X											
Demographics, medical history and previous treatment	X											
Therapeutic MIBG												
200mCi MIBG-  I IV administration			X				X		X		X	
Clinical safety assessment												
Physical exam		X	X	X	X	X	X	X	X	X	X	X
Vital signs, body weight and ECOG		X	X	X	X	X	X	X	X	X	X	X
Signs and symptoms assessment		X	X	X	X	X	X	X	X	X	X	X
Adverse Event Assessment		X		X	X	X	X	X	X	X	X	X

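### The 40% and 67% planning rates are not tied to the primary endpoint as defined, and with no stated test or cut-off the claimed 80% power for N = 22 is not established

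*Combined protocol and SAP*

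**What the plan says.** **Planning rates.** The Abstract states "we consider the H0 of DCR in 6 months of 40% (placebo arm of phase III studies in TNE), H1 as 67" (per cent). The Statistical plan states "we considered the 40-month disease control rate H0 to be 40" (per cent), takes it from placebo arms of phase III trials with one named example, and sets the alternative at 67%. Error rates are "Two-tailed type I error margin of 10%, power of 80" (per cent), with 10% loss, giving 22 patients in a single-arm, single-stage design.

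**Endpoint.** The three descriptions differ:
- Abstract: "The primary outcome will be the disease control rate (DCR) at 6 months after the end of treatment, per RECIST 1.1".
- Objectives, Primary: radiological control and, as a second primary objective, "Control of clinical/biochemical (functional NET) at 6 months after the end of treatment".
- Outcomes, Primary: radiological control and, for functioning tumours, also a GINET21 gain of at least 10% and markers that are stable or falling.

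The Inclusion criteria admit functional tumours. The expected share is not given.

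**Analysis.** The Statistical plan says "Descriptive statistics will be used to report population characteristics, binary outcomes and adverse events". It names no test of the primary rate against 40% and no number of successes that would make the trial positive.

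**The concern.** With one arm, the 40% benchmark is the only comparator. It has to describe the same endpoint, at the same time and in comparable patients, as the rate the trial will observe. Three things stand in the way.

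- The statistical section gives the benchmark a time label that disagrees with the Abstract.
- The endpoint has a radiological-only form and a composite form. The one named source of the benchmark is, by its title in the References, a trial in non-functional tumours, where the composite conditions would not apply. The 67% is given no derivation for either form.
- Without a test and cut-off, the power claim cannot be checked, and success could be declared at different counts.

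At stake is whether a result near the boundary would count as positive, and whether a negative result reflects lack of activity or a benchmark that does not belong to the endpoint.

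**Working it through.** **1. Reproducing N.** Inputs from the Abstract and Statistical plan: p0 = 0.40, p1 = 0.67, two-sided alpha 10% (z = 1.645), power 80% (z = 0.842), loss 10%.

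n = [1.645·√(0.40·0.60) + 0.842·√(0.67·0.33)]² / 0.27² = (0.806 + 0.396)² / 0.0729 = 19.8. Then 19.8/0.9 = 22.0. The plan's figure reproduces.

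**2. What 22 delivers with an exact test.** Exact binomial upper tails at 40% (alpha) and 67% (power):

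| Evaluable | Successes needed | Upper-tail alpha | Power at 67% |
|---|---|---|---|
| 22 | ≥14 | 0.021 | 72% |
| 22 | ≥13 | 0.055 | 85% |
| 20 | ≥13 | 0.021 | 67% |
| 20 | ≥12 | 0.057 | 82% |

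The cut-offs that stay within 5% fall short of 80% power. Those that reach 80% slightly exceed 5%.

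**3. The 40-month label.** The Introduction reports "progression-free survival of approximately 40 months versus 8.5 months for the group treated only with LAR octreotide monthly". On a constant hazard, a median of 8.5 months leaves 0.5^(40/8.5) = 4% progression-free at 40 months. That control arm had octreotide, not placebo, but a 40% rate at 40 months is out of keeping with it. The label is almost certainly a slip.

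**4. The added conditions.** Let f be the functional share and q the chance that a radiologically controlled functional patient also meets the quality-of-life and marker conditions. The documents give neither. Assume 40% and 67% are radiological rates, the same in functional and non-functional patients, with q the same under both hypotheses. Both rates are then multiplied by 1 − f + f·q.

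For illustration, f = 0.5 and q = 0.7 give a factor of 0.85:
- alternative: 0.67 × 0.85 = 57%
- matching null: 0.40 × 0.85 = 34%
- exact power against 40% at n = 22, true rate 57%: 34% at ≥14, 51% at ≥13
- chance of success at n = 22 if the true rate is the matching null of 34%: 0.4% at ≥14, 1.4% at ≥13

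Under these assumptions, testing against 40% protects type I error and costs power.

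**The case against.** **The planning rates may already be endpoint rates.** In the Abstract, the 6-month wording follows shortly after the primary outcome and reads naturally as shorthand for it. I accept that as the likeliest reading. The Cost-effectiveness section says "67% of patients will obtain disease control lasting at least 12 months", which looks like a third time label. But with 8-week cycles a fourth dose falls at week 24, and six months later is (24 + 26.1)/4.348 = 11.5 months from day 1, so the two nearly coincide. The cited MIBG series (65%, 75% and 80% in the Introduction, 63–80% in Table 1) also bracket 67%. None is reported at this landmark or on the composite, but the figure is not arbitrary.

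**A reader might infer a collapse in power from timing.** If 67% is a 6-month rate from the first dose, a constant hazard takes it to about 49% at the landmark (half the patients on 3 cycles, half on 4), and power against 40% falls to 13% at ≥14 or 24% at ≥13. The documents do not support that inference, because it ages the alternative and leaves the null alone. On the same reading the null falls to about 20%, and 20% versus 49% at n = 22 has 84% power at ≥9 (alpha 0.020).

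**The Outcomes section may be taken as operative.** The two primary objectives then map onto its two parts, and the Abstract is only a summary. That is reasonable, but it makes the composite the primary endpoint, to which neither rate is tied.

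**A two-sided 10% test need not be split equally.** An exact test that orders outcomes by probability would accept 13 of 22 (0.055 + 0.027 = 0.082), giving 85% power. It would not accept 12 of 20 (0.057 + 0.051 = 0.108). So 80% is attainable under one choice of test if all 22 count, which is a reason to name the test.

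**The population mismatch rests on one title.** The plan offers that trial only as an example. This limits how much weight the mismatch can bear.

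**Conclusion.** The point holds, as a gap between the sample-size basis and the endpoint. It is not an arithmetic error: a reader might infer that 22 is miscalculated, and it is not.

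Established from the text: the 40-month label conflicts with the Abstract, the primary endpoint has a radiological-only and a composite form, neither rate is linked to the composite, and no test or cut-off is stated. Established by calculation: with the upper tail held to 5%, exact power at a plain 67% is 72% with 22 patients and 67% with 20.

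Not established: the power lost through the composite. The 34% and 51% figures rest on an assumed functional share and an assumed chance of meeting the extra conditions, and only show that the effect could be material. Nor do the documents support saying that a positive result would be unreliable, since the added conditions push the true null below 40%. Confidence is high on the inconsistencies and the exact-test figures, and low on the size of the mismatch effect. This should be fixed before analysis.

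**What to change.** 1. Correct the 40-month label in the Statistical plan.
2. Reconcile the Abstract, Objectives and Outcomes into one primary endpoint. Whether it is radiological only or the composite is the sponsor's choice. State that the six months run from the last dose, if that is meant.
3. Give the null and alternative rates, with sources, for that endpoint at that time point. If the composite is kept, include the expected functional share and the basis for meeting the added conditions.
4. Name the exact test, how the two-sided 10% is allocated, and the number of successes required. Restate the power that 22 patients deliver, and 20 if losses are excluded.

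The cost is protocol and SAP wording plus one recalculation, with no added patients or scans. The sourced rates are not in the documents and must come from the sponsor. The downside is that the restated power may fall below 80%.

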## **Introduction**

Neuroendocrine tumors (NET) are rare neoplasms, but with increasing incidence and prevalence in the last decades. In more than half of the cases, they present metastatic and incurable at diagnosis. Few effective therapies are approved for these tumors (somatostatin analogues, everolimus, and sunitinib), none have demonstrated gains in overall survival, and none is approved in the Brazilian public health system (SUS).

Well-differentiated NET express, in more than 80% of the cases, somatostatin receptors. Somatostatin analogues, lanreotide or octreotide, have anti-proliferative and anti-secretory activity, and, frequently, are considered the first-line treatment in the metastatic setting. Somatostatin receptors expression, through scintigraphy scan marked with radionuclide and octreotate (Octreoscan©) or positron emission tomography labelled with Ga (Ga-PET-CT), is mandatory to effectively indicate the treatment with Lutetium^177 radionuclide. The NETTER-1 study demonstrated the efficacy of Lutetium^177, a type of peptide receptor radionuclide therapy (PRRT), in combination with long-acting releasing (LAR) octreotide 30 mg in second-line, with progression-free survival of approximately 40 months versus 8.5 months for the group treated only with LAR octreotide monthly in patients with midgut NET metastatic (HR: 0.20;  $p < 0.0001$ ). The NETTER-1 study established one more therapeutic strategy to NET, the PRRT.

However, invariably, metastatic NET patients develop disease progression to standard treatment. Different chemotherapeutic regimens (FOLFOX, cisplatin/etoposide, cisplatin/irinotecan, capecitabine/oxaliplatin, and capecitabine/temozolomide), hepatic debulking surgery, and interferon alpha are used based on small phase 2 trials and/or retrospectives studies. In the Brazilian consensus of NET, these treatment modalities, even with low evidence level, are recommended when there are no other effective treatments available. Although some patients could benefit from these therapeutic options, the results relating to tumor response and quality of life tend to be modest and the toxicity significant (Table 1). Therefore, new treatment should be investigated in this context.

The role of other PRRT therapies for NET has been the focus of research with new radiopharmaceuticals. Scintigraphy exam with I or I-metaiodobenzylguanidine (MIBG) is the standard for the staging and therapeutic planning of patients with paraganglioma/pheochromocytoma (PggF), a rare type of NET. Metaiodobenzylguanidine is molecularly analogous to norepinephrine and, therefore, is used in exams and treatment in these tumors of origin in sympathetic and parasympathetic neural ganglia. Patients whose tumors show positive uptake on the MIBG-I exam are treated with therapeutic doses of MIBG-I. The radiolabelled norepinephrine/norepinephrine analogue is injected intravenously, reaching target cells and emitting Beta radiation within them. In patients with metastatic PggF, therapy with MIBG-I

demonstrates objective tumor response rates of 30% and 50% of biochemical response in PggF. In 2018, at the American Society of Clinical Oncology (ASCO) congress, the first clinical study with PRRT with a noradrenaline analogue in patients with PggF, AZEDRA® (iobenguane I), was presented. In this study, 88 patients with metastatic PggF received a maximum dose of 18.5 GBq (500 mCi every 3 months twice). The primary outcome was the proportion of participants who reduced at least 50% of antihypertensive medications for at least 6 months; secondary outcomes were response rate and survival. The study was positive (25% decreased the use of antihypertensive medications), the median overall survival was 17.5 and 48.7 months in the participants who received one or two doses of treatment, respectively. Adverse events were considered manageable, the most common of which were haematological (mainly thrombocytopenia), fatigue and nausea.

Retrospective studies demonstrated that 50% to 60% of patients with gastroenteropancreatic (GEP) NET may have tumors with positive expression of MIBG-I, especially those with well-differentiated G1 and functioning tumors (producers of amines that cause clinical symptoms, such as carcinoid syndrome). Based on this information, it is intuitive to investigate the treatment with MIBG-I in other types of NET than PggF. In the largest series of cases, 211 patients with GEP or pulmonary NET treated with MIBG-I from 1994 to 2014, at the maximum dose of 18,500 MBq, had a median survival of 29 months since the start of treatment, 71% of clinical improvement with a median duration of 12 months and 20% with radiological response (80% disease control). Retrospective study with 38 patients with progressive NET GEP treated with a single dose of 7,400 MBq demonstrated 75% of radiological control of disease (3% of objective response), 63% with improvement of symptoms and median overall survival of 4 years. Toxicity was manageable, with 10% of transient neutropenia or thrombocytopenia and without complications. In another retrospective study of 38 patients with NET (most GEP NET [25 midgut]; one patient with lung NET and 4 with PggF), MIBG-I was administered at a dose of 5.5 GBq in three cycles at intervals of 10 to 12 weeks. The median progression-free survival was 13 months, the median overall survival was 48 months and the disease control rate was 65% (3 objective responses and 22 with stable disease). In terms of tolerability, only 2 patients (5%) had grade 3 myelotoxicity, which prevented the third application of MIBG-I. Another

retrospective study with 25 metastatic (17 NET) patients treated with MIBG-I with a cumulative dose of 27.7 GBq (751mCi) showed improvement in symptoms in 80% of cases and 48% of radiological response by WHO criteria. The median overall survival was 17 months since the last dose of MIBG-I, with a 5-year survival rate of 59%. Other studies have assessed the role of MIBG-I in controlling symptoms of refractory carcinoid syndrome. A retrospective study from the 1990s reported improvement in carcinoid symptoms in 14 out of 30 patients, with a median duration of 8 months.

Despite the encouraging data, the few existing studies have important methodological limitations, such as, heterogeneous population (patients with GEP NET and PggF in the same study), varied criteria for evaluating efficacy (WHO and RECIST) and eligibility (presence or absence of disease progression in the baseline; distinct types of tumors with different prognosis), varying doses of MIBG-I and do not report data on quality of life or symptom control prospectively.

Therefore, based on the premises that: (1) there is a need for research on rare neoplasms; (2) no effective systemic treatment for patients with well differentiated metastatic NET refractory to standard therapy; (3) GEP and lung NET may show positive expression in the MIBG-I123/131 scintigraphy exam, (4) data from retrospective studies suggest disease control and symptom improvement, but without data on quality of life and outcomes evaluated prospectively, (5) treatment of MIBG-I is available in the Brazilian public health system for the treatment of PggF, so there is no need for structural investment in the services that have this therapy, we propose a phase II study of MIBG-I for patients with GEP or pulmonary well differentiated NET with positive expression on MIBG-I scintigraphy.

